### b. Secondary outcome variables.

Generalized estimating equations (GEE) will be used to examine the difference between intervention and waitlist groups in change from baseline to 16 and to 32 weeks for fatigue and caregiver burden (secondary outcomes) using a similar approach (as described for primary outcome). We will use a similar approach to analyze cytokines and HRV. Given previous research in adults with chronic disease, we assume that the cytokine data will require log transformation to approach normality.

We compare differences in care recipient palliative care utilization, hospice enrollment, hospital admission, and mortality 6 months after caregiver completion of the intervention between intervention and control groups. We will use chi-square test to determine differences in rates of these outcomes and t-tests to compare average time to event between groups.

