### 2. Objectives

Aim 1: Test the feasibility and gauge an initial effect size of the intervention to improve QOL (primary outcome), fatigue and caregiver burden (secondary outcomes) among family caregivers from baseline to 16 weeks.

Aim 2: Test whether fatigue and caregiver burden are associated with a physiological measure of resilience, inflammatory cytokines (IL-6 and IL-10) detected in sweat patches and a self-reported measure of resilience, controlling for covariates.

Aim 3: Evaluate changes in heart rate variability (HRV), an indicator of physiologic stress, pre- and post-intervention.

Aim 4: Describe care recipient 6-month palliative care utilization, all-cause hospitalization, and mortality, comparing intervention and control.

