### 3. Background

Heart failure (HF) is a syndrome of multiple chronic symptoms and commonly co-occurs with 10 other chronic conditions. Nearly 30% of patients who have been hospitalized for HF will be readmitted within 30-60 days and 53% of patients hospitalized for HF will die within 5 years. As older adults manage worsening HF, caregiving responsibilities often increase, a phenomenon that has a greater impact among vulnerable populations. Throughout the provision of care, family caregivers must address a wide range of patient needs: assistance with everyday activities, help with a range of healthcare activities, transitions between settings of care, medication management and wound care. **However, because family caregivers are not routinely assessed in health care delivery, little is known about the context of their contributions to health care activities or the caregiving-related effects they experience.**

Previous studies of family caregivers of patients with HF have identified worsening quality of life (QOL) over the course of the patient's illness. For patients, being able to stay in the home as HF worsens, provides a sense of security, freedom and improved symptom awareness. However, many caregivers report increased distress while supporting the patient in the home, feeling alone and fully responsible for care. Fatigue and burden have been found to be significantly associated with decreased QOL, demonstrating the need to improve caregiver outcomes. Additionally, caregivers of patients with high symptoms perceive they spend more time on difficult tasks, have worse affective symptoms, and have poorer physical health-related QOL than those caring for patients with low symptoms. Thus, there is great need to provide interventions that improve QOL and decrease fatigue and caregiver burden of family caregivers of patients with HF, particularly in the home when patient symptoms are high.

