### **Johns Hopkins Bayview Clinic Recruitment:**

We will distribute a recruitment flyer in the heart failure clinic at the Johns Hopkins Bayview Medical Center. Caregivers that respond to the recruitment flyer will be screened for eligibility. If they are eligible, we will contact them by phone to explain study procedures. If interested in participating, we will schedule the caregiver's baseline interview within 10 days of initial contact. During the baseline interview the research assistant will re-explain the study, obtain written consent (if interview is in-person), or e-consent (if the interview is by phone or DoxyMe or Zoom video call).

**Overview of Study Design (Figure 2):** We propose an open label pilot (n=5) with a subsequent single-blind, two group randomized pilot trial to test the feasibility and gauge an initial effect size of the Caregiver-Support intervention to improve QOL. The immediate intervention group (n=20) will receive the intervention during weeks 0-16. The waitlist control group (n=20) will be provided written materials with community resources for caregivers during the first 16 weeks, then they will begin the intervention. Waitlist

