## **Open Label Phase:**

The first five participants will be enrolled into an open label pilot study, in which they will automatically receive the Caregiver-Support intervention. The participants will be interviewed after program completion to get feedback on the data collection instruments, intervention content including the number of visits and user-friendliness of intervention components (e.g. purpose in life activity), and satisfaction with the overall program process. This feedback will be used to modify the Caregiver-Support intervention for the waitlist control trial that will begin enrollment following the open label phase.

**Randomization:** Within 48 hours of the baseline interview, we will randomize using redcap randomization and communicate the assignment to participants by letter. At that same time, we will inform the nurse interventionist of the new participant. The intervention nurse will contact the participant within one week to schedule the first appointment. The waitlisted group will receive usual care for caregivers for the first 16 weeks, which is normally limited to inclusion in some clinical assessment and teaching during patient visits. Waitlisted participants will receive monthly study postcards to encourage retention. After 16 weeks, they will begin the intervention. The 32- week assessment will measure whether immediate intervention participants continue the strategies on their own and whether they continue to improve on the self-report scales and will measure improvement following the intervention for waitlisted participants.

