**Table 3: Study Visit Timeline for Immediate Intervention Group\***

Format and timing of visits	Key activities
Baseline Data Collection	Sweatpatch application Heartrate Variability Measurement Survey
Sweatpatch Pickup	72 hours post-application, remove sweatpatch and deliver for storage and analysis
Randomization	Mail randomization results
Home Visit Week 1	Assessment Set goals and discuss priorities Remove sweatpatch and deliver for storage and analysis (if not already performed)
Home Visit Week 3	Purpose in Life activity Instrumental Support activity: Benefits Check Up Assess goal attainment and revisit strategies
Phone Check-in Week 4	Review/edit purpose statement Assess goal attainment and strategies to achieve goal
Home Visit Week 6	Social Support Activity Assess goal attainment and strategies to achieve goal Follow-up re: instrumental support
Phone Check-in Week 8	Review/edit purpose statement Assess goal attainment and strategies to achieve goal
Home Visit Week 10	Assess goal attainment and strategies to achieve goal Follow-up re: instrumental and social support
Phone Check-in Week 12	Review/edit purpose statement Assess goal attainment and strategies to achieve goal
Home Visit Week 14	Review of progress, goals and purpose Discuss how caregiver will involve social support in next goals
Data Collection Visit Week 16	Sweatpatch application Heartrate Variability Measurement Survey
Sweatpatch Pickup	72 hours post application
Data Collection Visit Week 32	Sweatpatch application Heartrate Variability Measurement Survey
Sweatpatch Pickup	72 hours post application

\* Waitlist control group will begin intervention at week 16.

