**Table 4: Constructs, Instruments and Reliability**

Theoretical Construct	Instruments and variables	Number of Items	Cronbach's alpha
Caregiver demographics and characteristics	Demographics Characteristics: Caregiving physical and supportive tasks description, employment Physical Activity Readiness Assessment	23	-
Fatigue	PROMIS-Fatigue Short form	7	0.9 
Caregiver Burden	Oberst Caregiver Burden Scale 2 domains: time caregiving and task difficulty	15	0.90 
	Modified Caregiver Strain Index	13	0.86 
	ENRICHED Social Support	7	0.89 
Social Support	Family Functioning – Family Assessment Device Questionnaire: Global Family Functioning Scale (only)	12	0.9 
	Sweatpatch (IL6, IL10)	-	-
	Coping Self-Efficacy Scale	13	0.91 
Resilience	Heart Rate Variability	-	-
	Brief Resilience Scale	8	0.91 
Quality of Life	36-Item Short Form Health Survey (SF-36) 2 scales: Affective well-being and Physical health	36	0.85 
Depression	PHQ-8	8	0.82 
Care Recipient Palliative Care Utilization	Palliative care referral or encounter in electronic medical record within 6 months after caregiver completion of intervention	-	-
Care Recipient Hospitalization	Hospitalization (admission) encounter in electronic medical record within 6 months after caregiver completion of the intervention	-	-
Care Recipient Mortality	Documented as deceased in electronic medical record within 6 months after caregiver completion of the intervention	-	-
Care Recipient Hospice Enrollment	Enrollment in hospice in the electronic medical record within 6 months after caregiver completion of the intervention	-	-

**Data collection and management:**Questionnaire Data:

Trained research assistants will verbally elicit questionnaire data from participants in person or in virtual meetings. Virtual meetings include either telephone conversations or video calls via DoxyMe or Zoom. DoxyMe is a HIPAA compliant virtual meeting software used for telehealth purposes. We have created a HIPAA compliant Zoom account for video calls as well. Research assistants will directly enter data into the RedCap data entry and management system.

Due to COVID-19 research restrictions we will not collect sweat patch or HRV data until approved by the School of Nursing research restart committee.

Sweat patch:

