#### Care Recipient Data:

Six months after the caregiver completes the intervention, trained research assistants will search the electronic medical record of the caregiver's care recipient related to palliative care utilization (referral), hospice enrollment, hospitalization (admission), and death. Research assistants will directly enter data into the RedCap data entry and management system.

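### Aim 4's care-recipient outcomes are anchored at caregiver completion, so the intervention-versus-control tests do not compare the intervention with usual care

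*Combined protocol and SAP*

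**What the plan says.** Aim 4 (section 2) sets the task: "Describe care recipient 6-month palliative care utilization, all-cause hospitalization, and mortality, comparing intervention and control". It names no starting point for the 6 months.

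The operational text does name one, and it is the same everywhere:
- Table 4 ties all four care-recipient outcomes to completion. Mortality, for example, is "Documented as deceased in electronic medical record within 6 months after caregiver completion of the intervention".
- Care Recipient Data, in section 4: "Six months after the caregiver completes the intervention, trained research assistants will search the electronic medical record".
- Section 7.b compares the outcomes, including "mortality 6 months after caregiver completion of the intervention between intervention and control groups", using chi-square tests for rates and t-tests for time to event.

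The control arm is a waitlist. Overview of Study Design states: "The immediate intervention group (n=20) will receive the intervention during weeks 0-16". For the waitlist arm, the Randomization paragraph says "After 16 weeks, they will begin the intervention", and the Table 3 footnote says "Waitlist control group will begin intervention at week 16". The section 4 justification for a non-treatment group confirms that both arms are treated. It gives comparison with usual care as the reason for the waitlist.

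**The concern.** A comparison with usual care needs follow-up during which one arm is on usual care and the other is not. In this design that exists only in weeks 0-16. Because the clock starts at each caregiver's own completion, the waitlist arm's clock starts after it too has been treated. What 7.b labels and tests as intervention versus control is then closer to immediate versus delayed intervention.

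The anchor is also a post-randomisation event. A caregiver who never completes has no index date, and the record search for that caregiver's care recipient is never triggered. The comparison is therefore conditional on completion. Section 7.c assigns analyses that use post-randomisation data to supplementary status, but 7.b does not treat this one that way.

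At stake is what an observed difference in admissions, palliative care use or deaths could mean. Neither a difference nor a similarity could be read as the effect of the intervention against usual care.

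**Working it through.** The plan states no figure to reproduce here, so the check is a timeline followed by one illustration.

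**Inputs.** The last intervention visit is at week 14 (Table 3), and the intervention period is weeks 0-16 (Overview of Study Design). The waitlist arm starts at week 16 (Table 3 footnote) and is on usual care until then (Randomization). There are 20 per arm. Section 3 gives 53% dead within 5 years of an HF hospitalisation. Assumptions: 6 months = 26 weeks, 52.18 weeks per year, and the same visit schedule in the waitlist arm.

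**Reading 1: a window after completion.** This is the natural reading of Table 4.

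Window = [start + c, start + c + 26], with c = 14 (last visit) or 16 (end of period).

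| Completion | Immediate (start 0) | Waitlist (start 16) | Usual-care weeks in waitlist window | Weeks common to both windows |
|---|---|---|---|---|
| c = 14 | 14 to 40 | 30 to 56 | 0 of 16 | 40 - 30 = 10 |
| c = 16 | 16 to 42 | 32 to 58 | 0 of 16 | 42 - 32 = 10 |

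Both windows lie wholly after the intervention. Events before the window opens are not counted: the first 14-16 weeks in the immediate arm and the first 30-32 in the waitlist arm, a difference of 16 weeks.

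**Reading 2: cumulative status at the search date.** A care recipient who died in week 10 is also recorded as dead when the search is made. Counted this way, follow-up is 40-42 weeks in the immediate arm and 56-58 in the waitlist arm. The waitlist total now includes its 16 usual-care weeks, but also 56 - 16 = 40 to 58 - 16 = 42 weeks during or after its own intervention.

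Illustration with no treatment effect and constant hazard:
- h = -ln(1 - 0.53)/5 = 0.151 per year
- Deaths per 20 by week w = 20 × [1 - exp(-0.151 × w/52.18)]
- Immediate: w = 40 gives 2.2; w = 42 gives 2.3
- Waitlist: w = 56 gives 3.0; w = 58 gives 3.1

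Unequal follow-up alone would thus give about 0.8 more deaths per 20 in the waitlist arm.

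**The same hazard under Reading 1.** Uncounted deaths before the window are 0.8-0.9 per 20 in the immediate arm (w = 14, 16) and 1.7-1.8 in the waitlist arm (w = 30, 32). Risk inside the window, given survival to its start, is 1 - exp(-0.151 × 26/52.18) = 7.25% in both arms. A constant hazard forces that equality, so it is not evidence that bias is absent.

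**Can small counts produce a nominal result?** Take 0 versus 4 events with 20 per arm. The uncorrected chi-square is 40 × (20 × 4)² / (20 × 20 × 4 × 36) = 4.44, p = 0.035. A handful of events could cross the 0.05 level in section 7, so the label on the test is not academic.

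**The case against.** The strongest reply is that nothing is hidden. Section 4 says both arms are treated, section 7 names the groups waitlist and immediate intervention, and *control* can be taken as an arm label. Aim 4 asks only for description, the outcomes are secondary, and 7.c warns that the pilot is unlikely to have adequate power. All of that stands and limits the weight of the point. It does not supply an untreated comparator, and 7.b goes beyond description by adding between-group tests.

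A second reply is that the wording of the death outcome allows a cumulative count, so it is too strong to say that no untreated time can enter. That also stands, and it is why both readings are worked above. It replaces one defect with another: unequal follow-up, with usual care making up only 16 of the waitlist arm's 56-58 weeks.

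Four stronger inferences are tempting, and the documents do not support them:
- *Bias in a known direction.* From "Nearly 30% of patients who have been hospitalized for HF will be readmitted within 30-60 days" and the eligibility rule of a hospitalisation in the last 6 months, a reader might infer that risk falls with time and that the earlier, immediate-arm window must look worse. The documents give no hazard shape and no distribution of time from discharge to enrolment. Under the cumulative reading with no effect, the excess falls in the waitlist arm instead.
- *About 0.30 × 20 = 6 readmissions per arm lost before either window opens.* This holds only if every caregiver enrols at discharge. Recruitment is by referral and flyer up to 6 months later, and the loss would affect both arms alike.
- *A care recipient's death or long admission prevents the window from opening.* The termination examples in the DSMB material do not say whose events they are, and the enrolled participants are caregivers.
- *Section 7.c makes the Aim 4 contrast evidence of effectiveness.* The only effect size the plan specifies is Hedges' g for the primary outcomes. Extending that statement to Aim 4 is an inference.

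**Conclusion.** The point holds. As written, the care-recipient analysis does not estimate intervention versus usual care on either reading of the window, and it leaves caregivers who do not complete without an index date. Under the natural reading it compares immediate with delayed intervention, in windows that start 16 weeks apart, with none of the waitlist arm's usual-care time included. Under the cumulative reading, follow-up differs by 16 weeks.

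The timeline rests on the waitlist arm keeping the Table 3 schedule from week 16. The death counts rest on a constant hazard drawn from a 5-year figure and are illustrative only. The direction and size of any bias are not established. The point is confined to a secondary, descriptive aim: the primary quality-of-life comparison at 16 weeks is made while the waitlist arm is still untreated. It should be fixed, but it does not threaten the trial's main result.

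**What to change.** In Table 4, Care Recipient Data and 7.b:
1. Start the outcomes and time to event at randomisation, for all randomised caregivers, analysed by assigned arm whether or not the intervention was completed.
2. Set one record-search date, counted from randomisation and the same in both arms, so that non-completers are included.
3. Report randomisation to week 16 as the only comparison with an untreated control.
4. Report 6 months from randomisation, labelled immediate versus delayed assignment, and state that the waitlist arm is in its intervention period for about 26 - 16 = 10 of the 26 weeks.
5. Keep any post-completion window as description only, labelled immediate versus delayed intervention, with completion defined and no test presented as intervention versus control.

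If the team will not re-anchor, the minimum is to relabel the contrast, say which reading of the window applies, and state the rules for non-completers and for events before completion.

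**Cost.** A short amendment and the same chart review with event dates recorded, plus a search for non-completers that the plan does not now trigger. If the post-completion description is kept, a common search at week 58 covers every window above when visits run to schedule. That is about 16 weeks later than now for the immediate arm. The real downside is information. The 16-week comparison would have few deaths (about 0.9 per 20 under constant hazard), mostly covers the period of intervention delivery, and is shorter than the 6 months in Aim 4. No anchor yields 6 untreated months in this design, so the results stay descriptive.

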**Blinding, including justification for blinding:**

Research staff performing outcome assessments will be masked to assignment. Prior to follow-up assessment, staff will use standardized language to instruct participants not to discuss their treatment allocation with staff.

Justification of why participants will not receive routine care or will have current therapy stopped: n/a

**Justification for inclusion of a placebo or non-treatment group:** Both groups will receive the intervention. We are using a waitlist design to have a comparison to usual care.

Definition of treatment failure or participant removal criteria: n/a

Description of what happens to participants receiving therapy when study ends or if a participant's participation in the study ends prematurely: n/a

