## 5. Inclusion/Exclusion Criteria

Screening:

- 1) Six-Item Screener; Callahan CM et al., 2003

To be eligible for inclusion caregivers must:

- 1) 18 years or older and
- 2) English speaking
- 3) Live with the heart failure patient or visit the patient at least 3 days per week to provide care or support.
- 4) Provide support to the patient for at least 1 Instrumental Activity of Daily Living
- 5) Care for a heart failure patient hospitalized in the last 6 months
- 6) Live within a 1 hour driving radius of the Johns Hopkins Hospital

Exclusion Criteria:

- 1) Caregivers with cognitive impairment using the six-item screener will be excluded. Severe Cognitive Impairment would make active participation in interviews and survey completion very difficult.
- 2) Non-english speakers will be excluded. Non-english speakers may have unknown needs that cannot be addressed with this intervention.

- 3) Caregivers with terminal diagnosis will be excluded as goal-setting at end of life may be different than without a terminal diagnosis.

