### c. Statistical plan including sample size justification and interim data analysis.

As a pilot study, the analyses will likely not have adequate power to detect significant differences. Therefore, effect sizes, rather than statistical significance will be examined for evidence of the effectiveness of the intervention. With a total sample size of 53 we will be able to estimate the effect size associated with the intervention. This effect size will be compared to the literature for similar interventions and used to estimate the needed sample size to a fully powered effectiveness trial. There will be no interim data analysis.

Understanding the factors that predict which intervention components are successfully implemented and for which participant subgroups will be critical for fine-tuning this multicomponent intervention for future proposals that will extend efficacy examinations and effect modification analyses. Acceptability of the intervention will be examined in multiple ways. We will examine percentages of people who stayed in each arm of the study and conduct numerous descriptive correlational analyses of the association between

the intervention compliance and other variables. These analyses will quantify intervention implementation by demographic and participant health variables. Analyses that utilize the post-randomization data (e.g. treatment compliance) will be evaluated in supplementary analyses. We will distinguish non-compliance with intervention from attrition or loss to follow-up, i.e. missing data. We will also use the participant satisfaction data to examine acceptability of the intervention.

d. Early stopping rules.

As this is a low-risk behavioral intervention pilot, we have not defined any early stopping rules.

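### Care-recipient event times are to be compared by t-tests of their averages, with no rule for people without an event, for death before a non-fatal event, or for when each arm's clock starts

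*Combined protocol and SAP*

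**What the plan says.** Section 7.b names two analyses for four care-recipient outcomes (palliative care use, hospice enrollment, hospital admission, death): "We will use chi-square test to determine differences in rates of these outcomes and t-tests to compare average time to event between groups".

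Table 4 limits each outcome to a fixed window. For admission it reads "Hospitalization (admission) encounter in electronic medical record within 6 months after caregiver completion of the intervention", and the other three have the same window. The data come from one chart search (Care Recipient Data): "Six months after the caregiver completes the intervention, trained research assistants will search the electronic medical record".

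On the arms, section 4 states "Both groups will receive the intervention" in justifying the control group. Table 3 places the last session of the immediate arm at "Home Visit Week 14", and its footnote says "Waitlist control group will begin intervention at week 16".

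The supplied text contains no rule for a care recipient with no event in the window, no mention of censoring or of any survival method, and no rule for death before a referral, hospice enrollment or admission. The one missing-data sentence, in section 7.c, separates non-compliance from loss to follow-up and does not address event times. Completion is not defined for caregivers who stop early, although 20% attrition is expected.

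**The concern.** A person without the event has no event time, so a mean event time does not exist for the whole group until a rule supplies one. Without a rule, the natural course is to average the times that were observed. That compares only those who had the event, a subset chosen after randomization by the outcome itself. All observed times are squeezed into the same 26 weeks, so a treatment that prevents or delays many events may barely move their mean.

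This matters because section 7.c says that "effect sizes, rather than statistical significance will be examined for evidence of the effectiveness of the intervention". The estimate, not a p-value, is what readers will take away.

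The start of the clock is a second gap. If it is caregiver completion, it starts about 16 weeks later in the waitlist arm, it does not exist for non-completers, and both arms have been treated by then. The origin decides who is counted in the chi-square as well as in the time comparison.

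**Working it through.** The plan states no event rate or power for these outcomes, so there is no planned figure to reproduce. What follows illustrates how the method behaves; it does not predict an effect.

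**Inputs**
- 20 per arm (Overview of Study Design); window W = 26 weeks (Table 4).
- Death: 53% by 5 years after HF hospitalization (Background). At an assumed constant hazard, h = −ln(0.47)/5 years = 0.00289 per week, the same in both arms.
- Admission: nearly 30% readmitted within 30–60 days (Background). Eligibility is "Care for a heart failure patient hospitalized in the last 6 months", so the last admission may be well before entry, and a lower rate is added. Hazard l = −ln(0.7) divided by 60 days, 30 days or 26 weeks.
- Assumed effect: l is halved in one arm.

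**Formulas**, with c = l + h
- Events-only mean: 1/c − W·exp(−cW)/(1 − exp(−cW))
- Restricted mean free of admission or death: R = (1 − exp(−cW))/c
- Mean with non-events and prior deaths set to 26 weeks: W − (l/c)(W − R)

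**Admission, weeks (arm v arm, then difference)**

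| 30% admitted by | Events only | Event-or-death restricted mean | Non-events at 26 weeks |
|---|---|---|---|
| day 60 | 10.55 v 11.67: 1.1 | 15.41 v 19.41: 4.0 | 16.09 v 20.21: 4.1 |
| day 30 | 8.51 v 10.55: 2.0 | 10.37 v 15.41: 5.0 | 10.90 v 16.09: 5.2 |
| week 26 | 12.07 v 12.45: 0.4 | 21.11 v 22.97: 1.9 | 21.96 v 23.87: 1.9 |

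The events-only difference is 1.13/4.00 = 28%, 2.04/5.03 = 40% and 0.38/1.85 = 21% of the composite difference. The two restricted means differ from each other by 0.2 weeks or less. The SE of the composite difference is 2.86, 2.80 and 2.33 weeks; multiplied by t(38) = 2.02, the 95% half-widths are about 5.8, 5.7 and 4.7 weeks. In the week-26 case an arm has fewer than 2 admissions in 16% of trials.

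**Death**
- 6-month risk p = 1 − exp(−26h) = 0.0725, or 20 × 0.0725 = 1.45 deaths per arm. About 18 to 19 of 20 have no time to death.
- A pooled events-only t-test fails if an arm has no deaths or if each arm has exactly one. With P0 = (1 − p)^20 = 0.222 and P1 = 20p(1 − p)^19 = 0.347, the probability is 1 − (1 − 0.222)² + 0.347² = 0.52.
- The same formula gives 73% at p = 5%, 30% at 10%, 9% at 15% and 3% at 20%.

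**Time origin**
- Immediate arm: last session at week 14. Waitlist arm on the same schedule: 16 + 14 = week 30.
- Expected deaths before the clock starts: 20(1 − exp(−14h)) = 0.8 v 20(1 − exp(−30h)) = 1.7 per 20.

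**The case against.** The strongest reply is that the t-test need not be wrong. The chart is searched after a fixed window has closed, so complete follow-up is intended. If everyone without the event is given 26 weeks, a t-test of the averages compares restricted means. This stands: the fault is the missing rule, not the t-test as such. A reader might infer that the sponsor will discard non-events. The documents do not say that; it is the plain reading of an average time to event, and the sizes above hold only on that reading.

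Second, the rates are borrowed and the halved hazard is assumed. This also stands, and the death result in particular depends on one converted mortality figure, hence the range. The missing rule itself needs no assumed rate.

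Third, Aim 4 only describes, in a pilot with no power target. That limits the importance of the point, but an estimate that hides most of a difference, or cannot be computed, is a poor description too.

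It is also tempting to say that the chi-square on rates is untouched. The documents do not support that: the undefined origin determines who is at risk when counting starts.

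**Conclusion.** The point holds for the time-to-event part of section 7.b. No rule covers non-events or prior death, and the plain reading gives a comparison that is misleading for admission and often incomputable for death. The sizes (20% to 40% of the event-free-time difference; about half of trials for death) rest on constant hazards, a hazard ratio of 0.5 for admission, and 6-month mortality of about 7%. No hospice or palliative care rate is given, so nothing is computed for those outcomes.

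The time-origin gap reaches the chi-square as well. From completion, the arms are both treated and about 16 weeks apart, so the result cannot be described as intervention versus usual care.

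A reader might infer that the trial's main result is at risk. It is not: the primary quality-of-life analysis does not use these data.

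**What to change.** 1. Replace the average-time comparison with the difference in restricted mean time to 6 months, with a 95% CI, including every care recipient. Use restricted mean survival time for death.
2. For admission, hospice and palliative care, state one rule for prior death: either the event-or-death composite, or non-events including prior deaths set to 26 weeks. The second counts those who die first as event-free, so say so; with complete records a Welch interval on those values is enough.
3. Censor at the end of the window for people with full record coverage, and earlier only where coverage is known to have ended. The last encounter is not a suitable censoring date for someone known to be alive and covered.
4. State the time origin for both arms and for care recipients whose caregiver does not complete. Apply it to the chi-square too, and report deaths before it by arm. If the origin stays at completion, do not label the result intervention versus usual care.
5. Record event dates, and any date on which coverage ended, at the chart review.

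The cost is SAP wording, a few lines of code and, if not already planned, date fields on the chart-review form; sample size, visits and intervention do not change. Choosing an origin other than completion could also mean changing the chart-review window, which is a larger decision. Estimates stay imprecise at 20 per arm: about ±6 weeks for admission and, at 7% mortality, ±2.5 weeks for death (SE 1.25 × 2.02).
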